9.3 Risk adjustment

9.3.1 Propensity Score Matching

For the planned analyses, patients with opioid and non-opioid treatment need to be comparable. Mortality rates are expected around 100 and 200 per 10,000 persons years⁸ thus limiting the number of covariates for risk-adjustment to avoid over-fitting (10:1 rule of thumb: Not more than 1 predictor/covariate for 10 events). To avoid this overfitting problem but still be able to adjust for a large number of covariates, a propensity score (PS) matching will be conducted before the acutual Cox regression.

PS-Matching will be based on logistic regression and reflect the probability of getting an opioid treatment considering the following risk factors. The choice of covariates is based on a previous retrospective cohort study about opioid dependency and mortality in the US⁹ (see Appendix A, for the list of study covariates based on Ray et al.)

- region (i.e. 'Bundesland')
- comorbidities: obstructive sleep apnoea, depression and other comordidities
- comedication with other anticonvulsants than gabapentin, pregabalin or carbamazepine, comedication with neuroleptics, NSAR, tranquilizer or muscle relaxants, metamizole, comedication

⁸ Numbers from Ray et al. (2016)

⁹ Ray et al., 2016

with cannabinoid drugs, year of index treatment and drug dosage of the opioids/non-opioids as defined in section 9.4.

- medical procedures based on OPS-codes assessed as a number of procedures (see Appendix B, for the list of OPS codes), e.g. dialysis

PS matching will be based on a logistic regression (logit model) and reflects the likelihood that a patient will be prescribed by opioid medication if certain risk factors/comorbidities are considered. All binary predictors are included in the model as dummy variables (1 vs. 0). The influence of each variable is given as odds ratios with 95% confidence intervals.

The following equation will be employed for PS matching:

$$P_i = \frac{e^{\beta_0 + \sum_{j=1}^n \beta_j x_{j,i}}}{1 + e^{\beta_0 + \sum_{j=1}^n \beta_j x_{j,i}}}$$

The dependent variable is the treatment and will be dummy coded as 1 (opioid treatment in index year) and 0 (no opioid treatment) (P_i).

Age and gender will also be used for risk adjustment and will be assessed using national insurance data, for age by date of birth and is calculated based on the index treatment. For age, a variance of 5 years is allowed, i.e. the age can vary by plus / minus 5 years when matching.

Finally, based on the propensity scores, matching will be performed using the GenMatch function of the R statistical package. The probability values p_i of the matched patients may vary by $\pm 0.2 * \text{standard deviation}$. This range is often used in PS matching using logistic regression, provides a balance of included covariates, and thus no large number of patients are lost because they are still treated as comparable for small deviations¹⁰.

¹⁰ Austin et al., 2011

The frequency matching will be performed by dividing the study cohort into 1 % centiles according to the long-acting opioid propensity score distribution¹¹. Within each centile, one patient that had a prescription of non-opioid treatment will be randomly selected to increase the likelihood that all matches have equal quality and permit an analysis with unmatched data.

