Exclusion criteria: Patients with previous prescription of opioid medication or non-opioid medication between 01.01.2012 and index treatment will be excluded. Patients with cancer treatment, palliative care or opioid substitution after index treatment will be excluded.

Follow-up: Patients' follow-up period include 5 years after start of opioid resp. non-opioid treatment and chronic pain diagnosis between 01.01.2013 and 31.12.2017. Each patient will be censored at death (death date), switching of study group (opioid --> non-opioid or vice versa), 12 months without treatment or followed-up 5 years until last known record for the patient in the German health claims database, latest at 31.12. 2017 (end of latest data cut), whichever happens first.

Variables:

Outcome Variables include death by any course as primary endpoint and hospitalization due to any course, hospitalization with misuse, addiction diagnoses, outpatient diagnosis of misuse or addiction and treatment procedures as secondary endpoints.

Exposure Variables are pain treatments including opioid and non-opioid treatments.

Other Covariates will be collected for assessments over the course of the study: Age and gender (sex: male, female), charlson comorbidity index. Comorbidities, comedications, region will be collected for Propensity Score Matching.

Data Analysis: The main analysis will focus on each of the 2 main cohorts with chronic pain patients as defined at inclusion and:

- with opioid treatment between 01.01.2013 and 31.12.2017 (named cohort A)
- with non-opioid treatment between 01.01.2013 and 31.12.2017 (named cohort B)

To address the group comparisons adequately, a propensity score matching will be conducted. The main analyses will include a multivariate Cox proportional hazards regression. Additional stratified analyzes will be carried out as follows: Subgroup analyses for each following pain conditions will be conducted: headache (R 51*); pain, not elsewhere classified (R52*); persistent somatoform pain disorder (F45.4*); polyneuropathy in diabetes (E10.4*-E14.4 plus G63.3), kyphosis and lordosis (M40), scoliosis (M41), spinal osteochondrosis (M42), other deforming dorsopathies (M43), ankylosing spondylitis (M45), other inflammatory spondylopathies (M46), spondylosis (M47), other spondylopathies (M48), and spondylopathies in diseases classified

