9.10.1.4 Confounding

Confounding occurs when a covariate is independently associated with the exposure and the outcome of interest. The size of the datasets should allow analysis to explore and control this bias satisfactory. Subgroup analyses of subpopulations with different chronic pain diagnoses will be considered. However, unmeasured confounding cannot be excluded.

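### The visible propensity-score and Cox covariate lists do not name the qualifying pain diagnosis, so the primary hazard ratio may be confounded by pain condition unless Appendix A already covers it

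*Protocol*

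**What the plan says.** **Population.** Section 9.2.2.1 and Table 9-2 of the protocol admit patients with headache, migraine and other headache syndromes, facial neuralgia and pain, somatoform pain, unspecified pain, polyneuropathy, diabetic neuropathy, or any code in M00-M99.

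**Propensity score.** Section 9.3.1 states: "PS-Matching will be based on logistic regression and reflect the probability of getting an opioid treatment considering the following risk factors". The list gives region, then "comorbidities: obstructive sleep apnoea, depression and other comordidities", then comedication, year of index treatment, dosage and number of procedures. For the covariate list it points to Appendix A, taken from an earlier US cohort study; that appendix was not in the text available here. The synopsis, under Variables, says "Comorbidities, comedications, region will be collected for Propensity Score Matching".

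**Matching conditions.** On age, "the age can vary by plus / minus 5 years when matching". On the score, "The probability values p_i of the matched patients may vary by" 0.2 standard deviations. A second description uses score centiles: "Within each centile, one patient that had a prescription of non-opioid treatment will be randomly selected". None of these mentions pain diagnosis.

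**Cox model.** Section 9.3.2 lists gender, age, Charlson index, treatment duration, quarter of index treatment and the propensity score, plus dosage as a time-varying term. It cites no appendix for these covariates.

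**Pain condition elsewhere.** Section 9.10.1.4, on confounding, says "Subgroup analyses of subpopulations with different chronic pain diagnoses will be considered". The synopsis and sections 9.7 and 9.8.1 do commit to analyses by pain condition; 9.8.1 calls its subgroups descriptive.

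**The concern.** The pain condition plausibly influences both whether an opioid is chosen and how likely the patient is to die. That makes it a candidate for confounding by indication, and one measured in the data, because the codes are extracted to establish eligibility. If it is in neither the score nor the outcome model, the matched cohorts may hold different mixes of pain conditions, and part of any mortality difference would reflect the mix.

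Subgroup analyses do not repair this. They show results within conditions but leave the primary hazard ratio as it was. In the pain-condition strata, the protocol does not say that covariate balance will be checked.

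**Working it through.** **1. Is pain diagnosis in the lists?**

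| Place | Pain diagnosis named? | Possible indirect route |
|---|---|---|
| Synopsis, Variables | No | Comorbidities, unspecified |
| 9.3.1, score covariates | No | Open-ended comorbidity item; Appendix A (not seen) |
| 9.3.1, matching conditions | No | None |
| 9.3.2, Cox covariates | No | Charlson index; propensity score, if the score contains it |

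**2. What does the Charlson index capture?** In Table 9-4, rheumatic codes including M05, M06, M32-M34 and M45 score 1 point. Diabetes with neurological complications (E10.4, E11.4, E13.4, E14.4) scores 2, pooled with other end-organ damage. Headache, migraine, R52, F45.4, G62 and most spinal codes score nothing. So some pain conditions are adjusted for, coarsely, and most are not.

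**3. Size of bias from one unadjusted diagnosis.** The protocol states no figure to reproduce and gives neither the prevalence of pain conditions by cohort nor their mortality ratios. All inputs below are assumptions. With prevalence pA (opioid) and pB (non-opioid), mortality ratio R and no true opioid effect:

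spurious ratio = [1 + pA(R - 1)] / [1 + pB(R - 1)]

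- 60% v 50%, R = 1.3: 1.18 / 1.15 = 1.03
- 60% v 40%, R = 1.5: 1.30 / 1.20 = 1.08
- 60% v 40%, R = 2.0: 1.60 / 1.40 = 1.14
- 70% v 30%, R = 2.0: 1.70 / 1.30 = 1.31
- Equal prevalence: 1.00

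More extreme inputs go further (50% v 20%, R = 3: 2.00 / 1.40 = 1.43). If the higher-mortality conditions were commoner among non-opioid patients, the bias would reverse (40% v 60%, R = 2: 1.40 / 1.60 = 0.88).

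**4. Does putting the diagnosis in the score help?** Simulation: 12 runs of 60,000 patients, true ratio 1, diagnosis prevalence 25%, odds ratio for opioid use about 2.2, mortality ratio 2, one further confounder, 1:1 matching within 0.2 SD of the score.

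| | Diagnosis left out | Diagnosis in score |
|---|---|---|
| Prevalence, opioid v non-opioid | 36.7% v 20.6% | 35.4% v 35.5% |
| Mean rate ratio (run-to-run SD) | 1.145 (0.072) | 1.005 (0.068) |
| Opioid patients with the diagnosis whose partner lacks it | 79.6% | 47.1% |
| Difference in the other confounder within the diagnosis stratum (SD units) | 0.016 | 0.001 |

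The standard error of the first mean is 0.072/√12 = 0.021, so 1.145 is not simulation noise. The formula in step 3 gives a similar value: 1.367 / 1.206 = 1.13.

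**5. What happens in the strata?** With the diagnosis in the score, 47.1% of opioid patients who have it are paired with someone who does not, yet the other confounder stays balanced within the stratum. In a further simulation whose score omitted an interaction, the within-stratum imbalance was modest, about 0.09 SD.

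**The case against.** The strongest objection is that the covariate list has not been seen in full. Section 9.3.1 defers to Appendix A and its comorbidity item is open-ended. If pain diagnoses are in Appendix A, the matched cohorts would be balanced on them on average, and the propensity score in the Cox model would carry them too. This stands, and it makes the point about the score conditional. It does not put pain diagnosis among the Cox covariates in its own right.

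Second, the calculation in step 3 treats the diagnosis as wholly unadjusted, whereas age, gender, Charlson index, comedication and procedures would absorb some of the effect. This also stands: the range is not a forecast of residual bias.

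Third, section 9.3.1 is wary of overfitting and allows one covariate per ten events. That bears on how many pain terms the Cox model can carry; the cost is worked out with the fix.

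A reader might go further and infer that the pain-condition strata are invalid because matched partners need not share a diagnosis. The protocol does not support that. Partners who differ on individual covariates are normal in propensity matching, and splitting pairs does not by itself lose balance if the diagnosis is in a well-specified score (step 5). The Cox model is not described as conditional on pairs, and 9.8.1 labels its subgroups descriptive.

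**Conclusion.** The point holds in a limited form. The visible score covariates and the Cox list do not name the qualifying pain diagnosis, the Charlson index covers it only in part, and the subgroup analyses cannot correct the primary result. Whether the score itself omits it depends on Appendix A.

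The illustrative bias of roughly 1.03 to 1.31 assumes prevalences of 50-70% in one or both cohorts against 30-50% in the comparator, mortality ratios of 1.3 to 2.0, and no help from other covariates. The true figure should be smaller after those adjustments, and the protocol does not settle its direction. It would be wrong to conclude that the overall hazard ratio compares different diseases: the supportable statement is that the cohorts may differ in their mix of pain conditions. This should be corrected, because the remedy uses data already extracted.

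**What to change.** 1. **Section 9.3.1.** State whether pain diagnoses are in the score. Unless Appendix A already includes them, add a pre-index indicator for each Table 9-2 group, with M00-M99 split into the planned subgroups. The synopsis (twelve categories within M40-M54) and 9.8.1 (M54 and M15-M19) differ, so fix one split.
2. **Section 9.3.2.** Add the same indicators to the Cox model, or stratify its baseline hazard by pain group. Stratifying needs a rule for patients with several diagnoses; indicators do not.
3. **Sections 9.7 and 9.8.1.** Check covariate balance within each pain-condition stratum, and re-match or adjust within it where balance fails. Exact matching on pain group is optional.

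**Cost.** Taking both subgroup lists, the M codes give 12 + 1 (M15-M19) + 1 (remainder) = 14 indicators. With the nine other Table 9-2 groups the total is 23. Under the protocol's rule of ten events per covariate, that needs 23 × 10 = 230 events. At its expected rates of 100 to 200 deaths per 10,000 person-years, this is 230/0.01 = 23,000 down to 230/0.02 = 11,500 person-years. The protocol gives no matched cohort size; if events are too few, merge small groups or use the stratified baseline hazard. Some matches may be lost in small pain groups.

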9.2.1 Study Period

Due to data protection regulations in Germany, only an extract of maximum 6 years of data coverage could be available for the research purposes: 1st January 2012 to 31st December 2017.

The **baseline period** is defined as the period prior to the date of first diagnosis of diagnoses or first opioid or non-opioid treatment initiation as described in inclusion criteria (Chapter 9.2.2.1). The baseline assessment period endures between January 01, 2012 and first study medication prescription.

Index treatment is defined as the date of first opioid or non-opioid treatment prescription between 1st January 2013 and 31st December 2017.

Exposure time is defined as time between index treatment and December 31, 2017. Considering data availability of a maximum of 6 years and prescription in a required time period of 60 months, exposure time endures maximum five years. Thus, patients can be censored at death (death date in the linked records), last known record for the patient in the German health claims database, switching of treatment groups (from opioid group to non-opioid group or vice versa), 12 months without opioid/non-opioid treatment or 31st December 2017 (end of latest data cut), whichever comes first.

[figure not shown]
The **outcomes** will be assessed between index treatment and 31.12.2017.

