9.2.2.2 Exclusion Criteria

Following exclusion criteria will be used to extract the eligible study population (see also Figure 2):

Cohort A and B:

- Patients with present opioid and non-opioid pain medication prescriptions in 2012 are excluded from analysis (therapy-naïve patients only).
- Cancer patients will be excluded if the cancer diagnosis is accompanied by at least one of the following treatments in the same quarter: radiation therapy or chemotherapy all defined by the codes in Table 9-3. Diagnoses will be assessed via ICD-10 diagnoses during the inclusion period from 1 January 2012 until index treatment and main and secondary hospital diagnoses (i.e. *Haupt- und Nebendiagnosen*) will be taken into account.
- Palliative care, coded by ICD-10 code Z51.5 or OPS code 8-982*, 8-98e*, 8-98h* before index date is excluded
- Opioid substitution treatment with ICD-10 code Z51.83 in the study period is excluded.

Table 9-3: Exclusion criteria for cancer patients

Name	ICD-10 Code	
Malignant neoplasms	C00-C97	
Plus at least one the following in the same quarter		
Name	Code	Type of Code
Palliative care	Z51.5	ICD-10
Chemo therapy	Z51.1	ICD-10
Radiation therapy	Z51.0	ICD-10
Chemo therapy	8-541* 8-542* 8-543* 8-544* 8-546*	OPS Code

Radiation therapy	8-52*	OPS Code
Palliative care	8-982* 8-98e* 8-98h*	OPS Code

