9.4.1 Exposure Assessment

Opioid and non-opioid treatments will be assessed using ATC and PZN codes (see Table 9-1) as described below:

- **Opioid Treatment** received between January 1st 2012 and December 31st 2016 in at least 3 quarters, over a 60-month period based on ATC code N02A%.
- **Non-Opioid Treatment** (NSAIDs, anticonvulsants, antidepressants) received between January 1st 2012 and December 31st 2016 in at least 3 quarters, over a 60-month period, based on ATC code in Table 9-1.
- **Treatment Dosage** will be assessed based on DDD assessment per ATC code using DIMDI data. Dosage will thus be calculated as medication dose per day based on the average prescription per year of the year. The number of medication claims, the number of drug packages and DDD per package are used to estimate the daily dose.

- Treatment dosage of opioid treatment will be defined based on morphine equivalence. The low dosage is thus defined as less than 60mg/d morphine equivalence. The intermediate dosage will be defined as a dosage between 60mg/d and 120mg/d morphine equivalence. The high dosage will be defined as 120mg/d morphine equivalence or higher.
- Treatment dosage for non-opioid treatment is defined as follows:
 - Anticonvulsive: based on gabapentin equivalence. The low dosage is thus defined as a daily dosage of less than 600mg/d gabapentin equivalents and a high dosage of 600mg/d or more gabapentin equivalents.
 - Antidepressants: via standard psychiatric dose according to AKDÄ (2006) recommendations: daily doses below the minimum standard psychiatric dose will be defined as "low", dosages above as "high". The standard psychiatric dose per ATC can be seen in Table 9-5.

Table 9-5:: Standard psychiatric doses as threshold for low/high dosage

Active substance	ATC code	Minimum standard psychiatric dose
Amitriptylin	N06AA09	100
Amitriptylinoxid	N06AA09	100
Clomipramin	N06AA04	100
Desipramin	N06AA01	100
Dibenzepin	N06AA08	240
Doxepin	N06AA12	100
Imipramin	N06AA02	100
Maprotilin	N06AA21	100
Nortriptylin	N06AA10	50

Trimipramin	N06AA06	100
Citalopram	N06AB04	20
Escitalopram	N06AB10	10
Fluoxetin	N06AB03	20
Fluvoxamin	N06AB08	100
Paroxetin	N06AB05	20
Sertralin	N06AB06	50
Moclobemid	N06AG02	300
Tranylcypromin	N06AF04	20
Venlafaxin	N06AX16	75
Duloxetin	N06AX21	60
Reboxetin	N06AX18	8
Mianserin	N06AX03	60
Mirtazapin	N06AX11	15
Trazodon	N06AX05	200

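### The propensity model for opioid versus non-opioid treatment includes the dosage of the index treatment itself, which is not a baseline covariate

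*Protocol*

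**What the plan says.** The propensity model in Protocol section 9.3.1 predicts treatment group: "The dependent variable is the treatment and will be dummy coded as 1 (opioid treatment in index year) and 0 (no opioid treatment". Its predictor list covers region, comorbidities, procedures and comedication "with cannabinoid drugs, year of index treatment and drug dosage of the opioids/non-opioids as defined in section 9.4".

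The timing comes from other sections:
- Section 9.2.1: "Index treatment is defined as the date of first opioid or non-opioid treatment prescription between 1st January 2013 and 31st December 2017". The same section closes the baseline window at that point: "The baseline assessment period endures between January 01, 2012 and first study medication prescription".
- Section 9.2.2.2: "Patients with present opioid and non-opioid pain medication prescriptions in 2012 are excluded from analysis". The exclusion criteria in the protocol's opening summary go further and bar such prescriptions at any time from 1 January 2012 up to index.

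Section 9.4.1 defines the dose: "Dosage will thus be calculated as medication dose per day based on the average prescription per year of the year". Opioids are graded in morphine equivalents at three levels, including "The intermediate dosage will be defined as a dosage between 60mg/d and 120mg/d morphine equivalence". Non-opioids have two levels on other scales: "Anticonvulsive: based on gabapentin equivalence", and a standard psychiatric dose for antidepressants. NSAIDs and metamizole have no dose classes.

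Section 9.3.1 allows matched scores to differ by 0.2 standard deviations. Section 9.3.2 also enters treatment dosage in the Cox model as a time-varying covariate, updated yearly.

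**The concern.** A propensity score should summarise what was known when treatment was chosen. The dose of the drug that was then prescribed is part of the exposure. Averaged over a year, it also reflects tolerability, response and survival after index.

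The same list in 9.3.1 limits anticonvulsant comedication to agents other than the three study anticonvulsants, which keeps those drugs out of the score. The dosage term brings them back.

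The protocol relies on this match to make the cohorts comparable before the Cox regression on all-cause death. Either the match cannot be formed, or it is formed on a variable that treatment has already affected.

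**Working it through.** The protocol gives no figure that depends on this term, so there is none to reproduce. The check has three steps.

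**1. Timing.** Under 9.2.1 and the opening summary, an included patient has no study-drug claim before index. A dose built from study-drug claims (9.4.1) therefore has no value in the baseline window. It first exists at index, and its yearly average uses later claims.

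**2. Class-specific scales entered as they stand.** The model's outcome is opioid treatment in the index year. A morphine-equivalent dose above zero in that year is the same fact as outcome = 1, so the model separates completely and fitted scores go to 1 and 0.
- Fitted scores average to the opioid share p, so their SD is at most √(p(1−p)).
- The protocol gives no cohort ratio. For assumed non-opioid to opioid ratios of 1, 2 and 4, the SD is at most 0.500, 0.471 and 0.400. The ceiling for any ratio is 0.5.
- The caliper is 0.2 × SD = 0.100, 0.094 and 0.080.
- The gap between the groups is 1.0, so no pair falls within the caliper.

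The frequency matching by 1% centiles in 9.3.1 does not help: after separation, at most the one centile that straddles the boundary can hold both groups.

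A simulated cohort agrees (assumed: 20,000 patients, one baseline covariate, caliper on the logit scale). With the baseline covariate alone, the AUC was 0.68 and 99.9% of opioid patients had a comparator in the caliper. With class-specific dose indicators added, the AUC was 1.00 and 0% had one.

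**3. A common dose measure.** Separation disappears, but the score now responds to what was prescribed. In the same simulated cohort, a high-dose flag generated from treatment alone had these odds ratios for opioid, at assumed high-dose shares (opioid vs non-opioid):
- 10% vs 40%: 0.16
- 30% vs 40%: 0.64
- 30% vs 30%: 1.01

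For the effect on the hazard ratio, let opioid patients differ by d SD in unmeasured severity, let severity and dose correlate at r within each group, and let treatment shift dose by s SD. The groups' mean doses then differ by rd + s. At equal dose, the remaining severity difference is d − r(rd + s) = d(1−r²) − rs. Take an assumed severity hazard ratio of 2 per SD, r = 0.5 and a true treatment hazard ratio of 1.0, and approximate the resulting hazard ratio as 2 to the power of the remaining difference:
- d = 0, s = −0.5: remaining difference 0 + 0.25 = 0.25. The hazard ratio is 2^0.25 = 1.19 with dose in the score and 1.00 without it.
- d = 0.5, s = +0.2: remaining difference 0.375 − 0.10 = 0.275. The hazard ratio is 2^0.275 = 1.21 with dose and 2^0.5 = 1.41 without it.

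Dose in the score can therefore add bias or reduce it.

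**The case against.** The strongest reply has four parts.

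- **Coding is unstated and may belong in a SAP; the covariate list in Appendix A is not visible.** This stands as far as it goes: total failure of matching belongs to one coding. It does not remove the instruction in 9.3.1 to include study-drug dosage. Complete separation would also show at the first fit, so the coding that runs unnoticed is the one that needs more care.
- **Dose may act as a proxy for severity and reduce confounding.** This is possible. With d = 0.5 and r = 0.5, the remaining difference is 0.375 − 0.5s, which is smaller in size than 0.5 whenever s lies between −0.25 and 1.75. But all these inputs are assumed, the dose is measured after the choice it should explain, and the class scales in 9.4.1 are not comparable.
- **Other codings exist.** In a pooled low/intermediate/high factor, the intermediate level is defined only for opioids and would be fitted at 1.0. A reader might infer that those patients cannot be matched. That does not follow, because matching is on the score: a non-opioid patient scoring at least 0.900, 0.906 or 0.920 (1 minus the calipers above) would qualify. A single ordinal numeric term produces neither this nor complete separation.
- **The index date is not settled.** Section 9.2.2.1 describes Cohort A by the start of opioid therapy, and 9.2.2.2 bars only 2012 prescriptions. If index were the first opioid claim, a Cohort A patient could have non-opioid claims, and hence a non-opioid dose, before index. This stands, so the point is confined to the dosage of the index treatment. Opioid dosage arises at or after index on either reading.

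**Conclusion.** The point holds. Under the protocol's own index, baseline and dose definitions, the dosage of the index treatment is an attribute of the treatment received, and its place among the propensity predictors is an error to correct before matching is run.

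The size depends on the coding. With class-specific scales and dose taken in the index year, no pairs form at any cohort ratio. With a common measure, matching proceeds and the bias is unknown in direction and size.

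Three stronger readings are tempting, and the protocol does not support them:
- That matching will fail outright. This needs the class-specific coding, which is nowhere stated.
- That the mortality hazard ratio will be biased in a particular direction. The illustrations go both ways and rest on assumed inputs.
- That NSAR and metamizole comedication must be zero for everyone at baseline. This follows only if index is the first prescription of any study drug, which 9.2.2.1 and 9.2.2.2 leave open.

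**What to change.** 1. In 9.3.1, delete study-drug dosage from the propensity model.
2. State that all remaining propensity predictors are measured only between 1 January 2012 and the day before index. Calendar year of index is fixed by the index date and is unaffected.
3. Reconcile the index definition: the opening summary's exclusion criteria and 9.2.1 on one side, 9.2.2.1 and 9.2.2.2 on the other. Only then decide whether NSAR and metamizole comedication can have a pre-index value and stay in the model.
4. In 9.3.2, leave treatment dosage out of the primary opioid versus non-opioid Cox comparison and report it in a separate exposure-response analysis. Changing 9.3.1 alone would leave post-index dose in the outcome model.

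The cost is wording changes in 9.3.1 and 9.3.2, with no new data. The small downside is losing post-index dose as a possible, though non-comparable, proxy for severity.

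### Section 9.3.1 fixes two matching procedures without ranking or linking them, and the second uses a score the protocol never models and gives no ratio per opioid patient

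*Protocol*

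**What the plan says.** All the relevant text is in Protocol section 9.3.1, Propensity Score Matching.

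- **Score.** A logistic model for treatment, with the outcome coded "1 (opioid treatment in index year) and 0 (no opioid treatment").
- **Age.** Handled next to the score, before either procedure is described: "the age can vary by plus / minus 5 years when matching".
- **First procedure.** "matching will be performed using the GenMatch function of the R statistical package". The tolerance follows: "The probability values p_i of the matched patients may vary by" 0.2 standard deviations either way. It is defended partly on the ground that few patients are then lost.
- **Second procedure.** "The frequency matching will be performed by dividing the study cohort into 1 % centiles", and this is done "according to the long-acting opioid propensity score distribution", with a footnote to the US cohort study from which the covariates were taken. The selection rule is that in each centile "one patient that had a prescription of non-opioid treatment will be randomly selected". The same sentence adds that this permits an analysis with unmatched data.

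The section places matching ahead of the Cox regression. No matching ratio is given for either procedure.

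**The concern.** Matching comes before the Cox model, so it determines which non-opioid patients enter the primary mortality comparison. Two procedures are each announced as the one to be performed. Neither is called primary or a sensitivity analysis, and no sentence says that one is nested in the other. An analyst could follow either paragraph and claim to have followed the protocol.

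The second paragraph has two further faults. It relies on a long-acting opioid score, which the protocol does not define, and it does not link the number of comparators drawn to the number of opioid patients in the centile.

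The data already exist. If the matching method is settled only after results can be seen, the primary hazard ratio is open to a choice that the protocol should have closed.

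**Working it through.** The protocol states no matched-set size, event count or power, so there is no figure of its own to reproduce. The check has three parts.

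**1. Do the two procedures accept the same pairs?**

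Inputs: tolerance of 0.2 SD and centiles of 1% (both section 9.3.1). Assumption, for illustration only: the score is normally distributed.

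- Width of a centile starting at p, in SD units: z(p + 0.01) − z(p).
- Share of the cohort inside the tolerance around a point c: Φ(c + 0.2) − Φ(c − 0.2).

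| Centile | Width (SD) |
|---|---|
| 50–51% | 0.025 |
| 10–11% | 0.055 |
| 5–6% | 0.090 |
| 2–3% | 0.173 |
| 1–2% | 0.273 |
| 0–1% | open-ended |

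At the centre the tolerance covers Φ(0.2) − Φ(−0.2) = 0.1585, about 16% of the cohort, or some 16 centiles. GenMatch may therefore pair patients many centiles apart, which the centile rule does not allow. In the other direction, two patients in the same centile always meet the tolerance except in the two outermost centiles at each end, where the width exceeds 0.2 SD. So the procedures overlap but are not the same rule.

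**2. Is the centile score the one that is modelled?**

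- Modelled: any study opioid (1) against no opioid (0).
- Used for the centiles: a long-acting opioid score.
- Table 9-1 lists seven study opioids and does not divide them into long- and short-acting.

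No long-acting score can be computed from the model that the section specifies.

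**3. What does the selection rule give if followed to the letter?**

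- Comparators: 100 centiles × 1 = 100 at most.
- Person-years at the 5-year maximum (section 9.1): 100 × 5 = 500.
- Deaths at the section's expected rates of 100 and 200 per 10,000 person-years: 500 × 0.01 = 5 and 500 × 0.02 = 10.
- With an assumed mean follow-up of 2.5 years: 250 × 0.01 = 2.5 and 250 × 0.02 = 5.

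The section's own rule allows one covariate per 10 events. Comparator deaths of 5 to 10 alone would carry at most one.

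If the sentence means one comparator for each opioid patient in the centile, the number of comparators equals the number of matched opioid patients. The protocol does not give that number. For an assumed 1,000 to 10,000 opioid patients it would be 1,000 to 10,000 comparators, which is 10 to 100 times the literal count.

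**The case against.** The strongest reply is that this is a missing phrase and not a rival analysis. Frequency matching normally means drawing comparators in proportion to the exposed patients in each stratum. The section wants few patients lost, and section 9.1 describes a 4-million-person extract. **This stands.** A reader might infer that the primary analysis would keep only 100 comparators and be left with almost no power. The text does not support that as the plan's intention, and power calculations built on it would describe an analysis that nobody is likely to run.

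Two other strong readings also fail.

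- *The centile step replaces GenMatch.* The protocol does not say so. A tolerance applied within centiles is conceivable, and most same-centile pairs would satisfy it. What can be shown is that the relation between the steps is unspecified, not that they are logically irreconcilable.
- *The centile step drops the age rule.* The 5-year tolerance is stated before both procedures as a general matching condition and is not part of the GenMatch description. Nothing removes it for the centiles. It only needs to be confirmed.

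It can also be said that the long-acting wording was carried over from the cited US study, whose title in section 14 concerns long-acting opioids. That is likely, but the rule still points to a score this study does not have.

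Finally, ratio and algorithm detail often sit in a statistical analysis plan. That would answer a protocol that left matching open. This one fixed two procedures and named the wrong score, and a later plan cannot follow both as written without choosing between them or inventing a link.

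**Conclusion.** The point holds. Section 9.3.1 gives two definitive matching procedures that are neither ranked nor linked, and they can yield different comparators for the primary Cox model. The centile procedure cannot be run as written, because its score is not modelled, and its selection rule lacks a ratio per opioid patient. This is a wrongly stated rule and not merely absent detail, so it should be corrected before any matching is done.

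The effect on the hazard ratio cannot be sized from the protocol, which gives neither cohort sizes nor a score distribution. The literal figures (at most 100 comparators, 5 to 10 comparator deaths over a full 5 years) show why the sentence needs correcting. They do not forecast the study's precision. The comparison of centile widths rests on an assumed normal score.

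**What to change.** Amend section 9.3.1 as follows.

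1. Name one procedure as the primary matching algorithm. Delete the other or label it a sensitivity analysis.
2. State the matching ratio per opioid patient. If centiles are kept, say that within each centile one non-opioid patient is drawn for every opioid patient.
3. Replace the long-acting opioid score with this study's opioid versus non-opioid score.
4. State that the 5-year age tolerance applies to whichever procedure is kept.

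The choice between the two procedures is the authors' to make, since either can serve once it is fully specified. The cost is protocol wording only, with no change to data extraction or follow-up.
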